3.2. Study Subjects

Unless otherwise noted, the **ITT** analysis set is the main analysis set used in the summarization of general (Study Population) analyses. Where specified additional summaries on the mITT-16w will also be presented.

3.2.1. Subject Disposition and Completion Status

The number of subjects screened for the study will be provided. A summary of study disposition will be provided by study treatment on all randomized subjects and mITT-16w analysis set separately showing the following:

- Number of subjects randomized
- Number of subjects treated
 - Number of treated subjects who completed the study
 - Number of treated subjects who discontinued early from the study
 - Primary reasons for early study discontinuation, with frequencies
 - Number of treated subjects who completed treatment
 - Number of treated subjects who discontinued treatment early
 - Primary reasons for early treatment discontinuation, with frequencies

The following disposition summary will be provided on the ITT set for Induction period:

- Number of subjects who completed the Week 8a Visit
- Number of subjects who discontinued prior to the Week 8a Visit
 - Primary reasons for discontinuation prior to the Week 8a Visit, with frequencies

A listing of subject disposition will include analysis set flags (ITT, Safety, mITT, mITT-16w, PP [Yes/No]), dates of first and last dose of study drug, primary reason for subject discontinuation of study treatment, study completion status, primary reason for study termination, and date of last contact.

A listing of subject eligibility (inclusion or exclusion criteria exceptions) and a listing of subjects randomized but not treated will be provided.

3.2.2. Demographic and Baseline Characteristics

Unless otherwise stated all Demographic and Baseline Characteristic tables will be summarized on the both the ITT and the mITT-16w analysis set. All listings will be presented for the Safety analysis set.

Demographics

Demographic data including age, sex, race, ethnicity, weight, height, and body mass index (BMI) will be summarized overall and by treatment group. Sex, race, and ethnicity frequency distributions will be provided.

Tobacco Consumption

A summary of Tobacco Consumption taken at baseline or screening will be provided summarizing:

Parameter	Units/Response category
Tobacco Consumption Status	Never, Current,

	Former
Number of Tobacco Units Per Day	Converted Units
Number of Years With Tobacco Use	Years
Total Number Of Pack Years	Pack Years
Type of Tobacco Product Used	Cigarettes, Cigars, Pipe, Smokeless Tobacco

The following conversion process is used to standardize a unit of tobacco consumption:

1 unit = 1 pack (20 cigarettes) = 5 cigars = 8 pipes = 8 pinches

Number of years of tobacco use is calculated as follows where current smokers use the Day 1 Visit date as end date:

$$\frac{(Tobacco\ use\ end\ date - Tobacco\ use\ start\ date + 1)}{365.25}$$

Pack Years is calculated as number of years of tobacco use multiplied by number of tobacco units per day (converted units).

A listing will also be provided.

Ulcerative Colitis Disease State Clinical Characteristics

A summary of Ulcerative Colitis Clinical Characteristics taken at baseline or screening will be provided. A listing will also be provided.

Parameter	Units/Response category
Severity of Disease	Moderate: $6 \leq tMS \leq 10$, Severe: $tMS > 10$
Time Since Diagnosis	Years
Time Since Diagnosis categories	≤ 5 years; > 5 to ≤ 15 years; > 15 years
Time since start of symptoms	Years
Extent or location of Disease	Proctosigmoiditis, Left-sided colitis, Extensive, Unknown
Presence of Complications	Yes, No
Normal stool count in remission or prior to diagnosis	Stools
██████████	████
████████████████████	██████
██████████	
████████████████████	████
████████████████████	██████
████████████████████	

Prior Ulcerative Colitis Therapy Characteristics

A summary of Prior Ulcerative Colitis Therapy Characteristics will be provided. A listing will also be provided.

Parameter	Units/Response category
-----------	-------------------------

Prior biologic failure	Yes, No
Prior biologic experience	Failed, Naïve, Experienced but no documented failure
Number of prior biologics failed	0, 1, 2, ≥ 3
Biologic classes failed	0, 1, 2, 3
Primary Non-responder to at least 1 Biologic	Yes, No
Secondary Non-responder to at least 1 Biologic	Yes, No
Inadequate Response to at least 1 Biologic	Yes, No
Intolerant to at least 1 Biologic	Yes, No
Oral corticosteroid use at enrollment	Yes, No
History of steroid non-response	Yes, No
History of steroid dependence	Yes, No
History of steroid dependence, non-response or intolerance	Yes, No
Prior immunomodulator use	Yes, No
History of immunomodulator non-response or intolerance	Yes, No
Prior aminosalicylate use	Yes, No
Aminosalicylate use at enrolment	Yes, No
History of aminosalicylate non-response	Yes, No
Prior Jak-inhibitor use	Yes, No

Complications of Ulcerative Colitis at Baseline

A summary of complications of ulcerative colitis at Baseline will be provided, the number and percentage of subjects with each complication collected on the Ulcerative Colitis History page will be presented. A listing will also be provided.

Baseline Mayo Scores

A summary of baseline Mayo scores and components will include the following items. A listing will also be provided.

Parameter	Units/Response category
Baseline tMS	Points
Baseline pMS	Points
Baseline aMS	Points
Baseline PRO2	Points
Baseline Mayo Stool Frequency subscore	0, 1, 2, 3
Baseline Mayo Rectal Bleeding subscore	0, 1, 2, 3
Baseline Mayo Endoscopy Findings subscore	0, 1, 2, 3
Baseline Mayo Physician Global Assessment subscore	0, 1, 2, 3

3.2.3. Protocol Deviations

Unique subjects reporting major protocol deviations that have significant impact on primary efficacy analyses (major analysis protocol deviations) will be summarized overall and by treatment group for the ITT set.

Major analysis protocol deviations include:

1. Subjects who received the wrong treatment prior to Week 8a visit,

2. Study drug compliance defined as compliance $< 80\%$ or $\geq 120\%$ during 8 Week Induction study,
3. Subject did not meet efficacy-related inclusion criteria (inclusion criterion 4 and 5),
4. Subject took a prohibited medication prior to Day 1 (exclusion criteria 7a-j),
5. Subject required prohibited concomitant medications that are deemed to have an impact on the efficacy outcomes

A subject listing with all protocol deviations identified prior to database lock will be provided. Moreover, a listing of all major analysis protocol deviations will be provided. All subject listings will be based on the randomized analysis set.

A summary and listing of COVID-19 protocol deviations will also be presented, along with a listing of COVID-19 impacts.

3.2.4. Medical History

Medical history data will be coded using the Medical Dictionary for Regulatory Activities, version # or later. The number and percentage of subjects with medical history coded to each system organ class and preferred term will be summarized by treatment group for the safety analysis set.

3.2.5. Prior/Concomitant Medications

Prior medications include all medications taken prior to the first dose of study drug, regardless of when they were stopped. Concomitant medications include all non-study medications that the subject was taking prior to the Day 1 visit that were ongoing at the visit, in addition to all medications with a start date on or after the first dose date and no later than the last dose date + 28 days. Medications with a start date after the last dose date + 28 days will not be included in summaries but will be included in the listing of concomitant medications, with a flag.

Recorded prior and concomitant medication names from the Prior and Concomitant Medications eCRF page will be mapped according to the [REDACTED]

Prior and concomitant medication use will be tabulated separately. Medications that stopped more than 60 days prior to screening will not be included in the prior medication summaries. The number and percentage of subjects who have taken each medication will be provided by study treatment.

On-going Ulcerative Colitis Medications of Interest at Baseline will also be presented. Ulcerative Colitis Medications of Interest include aminosalicylates and corticosteroids. Should a subject enter the study on prohibited biologics and immunomodulators these medications will also be presented.

On-treatment rescue medication use will be summarized. Rescue medications are medications to treat UC or AE of worsening UC and are categorized as :

- Initiation of oral corticosteroids or aminosalicylates

- Increase in oral corticosteroids or aminosalicylates dose above baseline
- Prohibited medications

3.3. Primary Endpoint(s) Analysis

3.3.1. Definition of Primary Endpoint(s)

The primary efficacy endpoint is defined as the change from baseline in Total Mayo score at Week 8.

3.3.2. Total Mayo Score (tMS)

The Total Mayo score (0-12 points) (Table 5) is the sum of four components: stool frequency (0-3 pts), rectal bleeding (0-3 pts), Mayo endoscopic (0-3 pts) and Physician Global Assessment (0-3 pts) subscores.

Additional information on derivation of stool frequency and rectal bleeding components from diary data can be found in Section 5.4.

If at least one component of the Total Mayo score is available then the score will be calculated. Missing components will be imputed through last observation carried forward (LOCF).

Table 5: Components of Total Mayo Score

Stool Frequency
0 point: Normal number of stools for patient
1 point: 1 to 2 stools per day more than normal
2 points: 3 to 4 stools more than normal
3 points: ≥ 5 stools more than normal
Rectal Bleeding
0 point: No blood seen
1 point: Streaks of blood with stool less than half the time
2 points: Obvious blood with stool most of the time
3 points: Blood alone passes
Endoscopic Findings
0 point: Normal or inactive disease
1 point: Mild Disease (erythema, decreased vascular pattern)
2 points: Moderate Disease (marked erythema, lack of vascular pattern, friability, erosions)

3 points: Severe Disease (spontaneous bleeding, ulceration)
Physician's Global Assessment (PGA)
0 point: Normal
1 point: Mild disease
2 points: Moderate disease
3 points: Severe disease

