The preparation for any endoscopic procedure is up to the discretion of the investigator. The endoscopic score from the screening procedure performed at screening Stage 2, assessed by a central reader, will be used for eligibility criteria. If possible, it is preferable that all endoscopic procedures for each subject are performed by the same endoscopist and using the same bowel preparation for all procedures after screening.

All procedures can be performed by the investigator or qualified designee using the institution's standard procedure with or without sedation (conscious sedation or general anesthesia) for endoscopic assessment of disease activity and for biopsies. All procedures will be recorded and the images will be uploaded to the central reader imaging platform. An endoscopic video instruction manual will be provided separately. The centrally read endoscopic subscore will be used for all endpoints and for eligibility criteria to enroll a subject into the Induction and Maintenance Studies. Local reading of the endoscopic subscore will also be collected. Of note, an endoscopic central reading charter has been developed to outline the central reading process.

Subjects may undergo approximately five endoscopic procedures, ([Table 1](#), [Table 2](#), and [Table 3](#)) during their participation in the studies (Screening, Week 8, Week 16 if applicable, CFA Visit 2 if applicable, mWeek 44). However, this may be more if multiple CFA Visit 2 assessments are completed. Up to six biopsies will be taken at each of the defined time points. These biopsies may be used for histology and evaluation of exploratory inflammatory biomarker levels (and potentially tissue PK for Phase 2b Induction Study). Biopsies should be performed at the location of the worst inflammation in the rectum and/or sigmoid during the Screening endoscopy. During subsequent procedures after Screening, every effort should be made to take biopsies in the same area as done during the Screening endoscopy regardless of the area of worst inflammation in the current endoscopy. The location of biopsy site must be recorded.

A biopsy manual will be provided with detailed instructions for biopsy site identification, sample collection, handling, and shipping. Biopsy sample collection kits will be provided.

[REDACTED]

[REDACTED]

[REDACTED]

[REDACTED]

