8.5.4. Primary Efficacy Evaluation

For efficacy evaluations, the null hypothesis for treatment comparisons will be that there is no difference between a given dose level of TD-1473 and placebo; the alternative hypothesis will be that there is a difference.

For primary endpoints of each study, missing data and sensitivity analyses will be performed. Further details will be given in each applicable SAP.

Phase 2b Induction:

The primary endpoint is reduction in total Mayo score at Week 8. An analysis of covariance (ANCOVA) model will be used with terms for the stratification factors, baseline score, and treatments, and each TD-1473 dose will be compared to placebo. Missing Week 8 scores will not be imputed.

Phase 3 Induction:

The primary endpoint is clinical remission at Week 8. Each active dose selected will be compared to placebo using a stratified Cochran-Mantel-Haenszel (CMH) test, stratifying by randomization stratum. Subjects with missing data or who meet a treatment failure criterion will be counted as not meeting the endpoint of clinical remission (Refer to Section 8.9).

Phase 3 Maintenance:

The primary endpoint is clinical remission at Maintenance Week 44. Each active dose selected for continued evaluation in the Maintenance Study will be compared to placebo using a stratified CMH test, stratifying by randomization stratum. Subjects with missing data or who meet a treatment failure criterion will be counted as not meeting the endpoint of clinical remission (Refer to Section 8.9).

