8.9. Data Handling Rules

For primary analyses of all applicable efficacy endpoints, including secondary and additional endpoints, the following rules will be applied. For sensitivity analyses of primary and key secondary endpoints, different rules may be specified in the applicable SAP.

- Binary endpoints: Subjects who had non-missing data for a binary efficacy endpoint meeting the criterion for success but met definition of treatment failure prior to visit will be considered as not meeting endpoint. Full rules for the derivation of treatment failure will be outlined in the SAP.
- Missing = endpoint not met

Quantitative or score endpoints:

- The treatment failure criteria above are applied to exclude any assessments obtained following treatment failure
- MMRM analysis with data assumed to be “Missing at Random” for quantitative or score endpoints assessed more than once postbaseline
- The analysis of the Phase 2b primary endpoint will be a completers analysis. For other quantitative or score endpoints assessed only once post-baseline, imputation for missing data will be described in the SAP.

[REDACTED]

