 - Perform key efficacy endpoint assessments (endoscopy, Quality-of-Life questionnaires, [REDACTED], [REDACTED], PGA) in-person as required, and if feasible. If an in-person visit is not feasible, the minimum assessment to be performed remotely include obtaining information for the PGA.
- Procurement of study drug by participants (or designee) from the site or shipment of study drug directly to participants for at home administration.
- Laboratory assessments using a suitably accredited local laboratory; for selected assessments such as urine pregnancy, home testing may be conducted.

COVID-19-Related Exclusion

The field of COVID-19-related testing (for presence of, and immunity to, the SARS-CoV-2 virus) is rapidly evolving. Additional testing may be performed as part of screening and/or during the study if deemed necessary by the investigator and in accordance with current regulations or guidance from authorities and standards of care.

Documentation

Document what relevant contingency measures are implemented, how restrictions related to COVID-19 led to changes to the study conduct, and how the study participant was impacted. Related documentation, either in source or systems (e.g. eCRF), should be labelled with the prefix “CV19.” Protocol deviations related to the pandemic should also be labeled as such with the “CV19” prefix.

Activities that require the appropriate documentation include, but are not limited to, the following:

- Missed, delayed, or modified visits and/or assessments;
- Study drug dosing modification, dosing interruptions, and discontinuation and withdrawal from the study;
- Other temporary measures such as those listed in this appendix;
- If a participant is excluded from the study due to recent COVID-19-related elements, the reason for screen failure should be documented in the CRF.

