3.3.4.3. Missing Data Handling

After accounting for intercurrent events and individual missing components (outlined in Section 3.3.2) all missing data (including data missing due to COVID-19) will be assumed missing completely at random (MCAR) and not imputed.

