5. SUPPORTING DOCUMENTATION

5.1. Appendix 1: Changes to Protocol-Planned Analyses

The endpoints and analysis have been updated follow the advice in ICH E9 (R1) addendum on estimands and sensitivity analysis in clinical trials to the guideline on statistical principles for clinical trials. As a result, endpoints following a treatment policy strategy no longer omit data meeting treatment failure criteria as outlined in the protocol section 8.9.

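### The Phase 2b SAP builds a Week 8 total Mayo score from as few as one component by LOCF, so a missing Week 8 endoscopy becomes the screening value, in conflict with the protocol's completers rule

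*SAP*

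**What the plan says.** **Protocol.** Section 8.5.4, on the Phase 2b primary endpoint: "Missing Week 8 scores will not be imputed". Section 8.9 adds: "The analysis of the Phase 2b primary endpoint will be a completers analysis". Neither section gives a rule for filling in a single missing component of that endpoint.

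**Phase 2b SAP.** Section 3.3.2: "If at least one component of the Total Mayo score is available then the score will be calculated". The next sentence fills the missing components by LOCF. Section 3.3.4.3 then opens with "After accounting for intercurrent events and individual missing components (outlined in Section 3.3.2) all missing data" and treats what remains as missing completely at random and not imputed. Component LOCF is therefore part of the primary analysis.

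**Endoscopy schedule.** Protocol Section 6.4.1.20 lists the procedures as "Screening, Week 8, Week 16 if applicable, CFA Visit 2 if applicable, mWeek 44". SAP Section 5.9 likewise has endoscopy only at baseline and Week 8. Inclusion criterion 4 requires a centrally read screening subscore of at least 2.

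**Declared changes.** SAP Appendix 1 (Section 5.1) reports one change, that "endpoints following a treatment policy strategy no longer omit data meeting treatment failure criteria". Component LOCF is not mentioned.

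**The concern.** A score with one measured and three carried components is not a completed Week 8 score, yet it enters the ANCOVA on the same footing as a fully measured one. For endoscopy the carried value can only be the pre-treatment one, unless an unscheduled procedure was done. Section 3.3.4.1 says data are analysed as collected, and a carried screening endoscopy was not collected at Week 8.

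Two routes to this pattern can be foreseen from the documents:

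- **Remote visits during COVID-19.** Protocol Appendix 11 says: "If an in-person visit is not feasible, the minimum assessment to be performed remotely include obtaining information for the PGA". Endoscopy cannot be done remotely.
- **Early discontinuation.** The Early Study Drug Discontinuation visit has a PGA and a diary review but no endoscopy (SAP Table 2). Section 3.1.3 exempts only the End of Study visit from windowing. The Week 8 window runs from Day 46 to the earlier of Day 71 or the end of induction, so an early discontinuation visit on or after Day 46 can supply a Week 8 score that contains the screening endoscopy.

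At stake is who enters the primary analysis, and with what value. The result also feeds dose selection (Protocol Section 8.11).

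**Working it through.** **1. The plan's own power figures.** Inputs from Protocol Section 8.2.1: 60 per arm, 2-point effect at each of three doses, SD 3 (alternative 3.5), Hochberg at 2-sided 5%. Method: simulation of 200,000 trials per case, four normal arms, t-tests against a shared placebo arm.

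- SD 3: 88.9% for all three doses and 98.4% for at least one (stated: 89% and above 98%).
- SD 3.5: 73.9% and 93.9% (stated: about 73% and about 94%).

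The stated figures reproduce and are not in dispute.

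**2. What LOCF does to one subject.** Carried Week 8 endoscopy = screening endoscopy, so endoscopic change = 0 whatever happened in the bowel. Stool frequency, rectal bleeding and PGA have Week 2 and Week 4 values, so for them LOCF would usually carry Week 4.

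**3. Effect on the treatment difference, equal missingness.** Let m be the proportion with missing endoscopy and e the part of the 2-point effect that sits in endoscopy. Neither is in the documents; both are assumed. Attenuation = m × e.

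- m = 5%: 0.05 × 0.4 = 0.02 to 0.05 × 0.6 = 0.03 points
- m = 10%: 0.10 × 0.4 = 0.04 to 0.10 × 0.6 = 0.06 points (2 to 3% of the effect)
- m = 20%: 0.20 × 0.4 = 0.08 to 0.20 × 0.6 = 0.12 points (4 to 6%)

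**4. Power for all three doses.** Same simulation, SD 3. Assumptions: 0.5 points of effect per component, SD unchanged by LOCF, missingness equal across arms and unrelated to outcome.

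| Missing | Completers: n per arm, effect, power | LOCF, endoscopy only: effect, power | LOCF, three components from baseline: effect, power |
|---|---|---|---|
| 5% | 57, 2.0, 86.8% | 1.975, 87.8% | 1.925, 85.8% |
| 10% | 54, 2.0, 84.3% | 1.95, 87.0% | 1.85, 82.1% |
| 20% | 48, 2.0, 78.5% | 1.90, 84.5% | 1.70, 72.9% |

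The LOCF columns keep n = 60. The last column is a worst case, because it ignores the Week 2 and Week 4 values.

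**5. Unequal missingness.** Assume mean endoscopic change of -0.9 on active and -0.4 on placebo, and a difference of -1.5 from the other three components (true total -2.00). Estimated difference = -1.5 - 0.9 × (1 - m_active) + 0.4 × (1 - m_placebo).

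- 5% active, 15% placebo: -1.5 - 0.855 + 0.340 = -2.015
- 15% active, 5% placebo: -1.5 - 0.765 + 0.380 = -1.885
- 10% in both: -1.5 - 0.810 + 0.360 = -1.950

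**The case against.** The case for leaving the SAP alone has five parts.

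- **The rule is not hidden.** Protocol Section 8.1 asks only that changes be described in the applicable SAP. Section 3.3.2 does so in the SAP body, and Section 1 of the SAP says its appendices are not a formal part of the signed document. This stands: a reader might infer concealment from the silence of Appendix 1, but what the documents show is an incomplete list of changes.
- **The conflict is partial.** Where no component is available, the SAP still imputes nothing, and the protocol has no explicit rule for a partly observed score and leaves missing-data detail to the SAP. The first half stands. But a completers analysis does not naturally include a subject with one component of four, and a SAP that fills in detail should not reverse the stated principle.
- **PGA-only scores are not shown to be likely.** Appendix 11 sets the PGA as a minimum. Stool frequency and rectal bleeding come from a daily home diary, so a remote visit would usually lose endoscopy alone. This stands.
- **Safeguards exist.** Section 3.3.5 repeats the primary analysis with components multiply imputed, Supplementary Estimand 1 does likewise, and Section 3.3.6.5 tabulates missing components. These expose the problem without changing the primary estimate. The Section 3.3.5 analysis also alters component LOCF and wholly missing scores together, so it does not isolate the effect of LOCF.
- **LOCF can keep more power.** With endoscopy alone carried it does (87.0% against 84.3% at 10%). Loss of power is therefore not the argument; the argument is that unmeasured values are analysed as measured.

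**Conclusion.** The point holds. The protocol's completers rule and SAP Sections 3.3.2 and 3.3.4.3 give different primary analyses for any subject with a partly observed Week 8 score, and under the SAP a missing endoscopy is analysed as no endoscopic change. That follows from the text and the visit schedule and needs no assumption about rates.

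The size rests on assumption. With an endoscopy share of 0.4 to 0.6 points and equal missingness, the shrinkage is 0.04 to 0.06 points at 10% missing and 0.08 to 0.12 at 20%. Protocol Section 6.6.2 allows replacement of treated subjects if more than 10% withdraw before or miss the primary visit, but that is a trigger and not a forecast of missing components.

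Three stronger readings are not supported. A reader might infer that the bias is always conservative; with unequal missingness it is not. A reader might infer that standard errors are understated; that is plausible for single imputation, but it has not been calculated here and nothing in the documents quantifies it. A reader might infer that the primary result is seriously distorted; the illustrations give a modest shift unless missingness is high or several components are carried from baseline.

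**What to change.** - **Section 3.3.2:** for the primary analysis, derive the Week 8 total Mayo score only when all four Week 8 components are present. Otherwise leave it missing, as the protocol states.
- **Section 3.3.5:** keep the Section 5.9 component-level multiple imputation as the missing-at-random sensitivity analysis already planned. Making it the primary method would itself depart from the protocol and would need declaring.
- **Appendix 1:** if component LOCF is wanted, make it a supplementary analysis, list it there and give the reason.
- **Section 3.4.6.1:** apply the same completeness rule to the change in adapted Mayo score, using its three components.

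The cost is SAP wording and one derivation. A few more scores become missing, with a small loss of power for all three doses: about 84% against 87% at an assumed 10% missing endoscopy, SD 3.
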